2.1.2 Investigation-related Procedure

Recruitment paths:

- Our internal database was accessed to see if any potential participants who fit the inclusion criteria are available.
- Referrals from hearing healthcare providers in the Kitchener and surrounding area were requested.

Tasks

Appointment tasks are listed in the table below.

Tasks per appointment visit.

Visit 1	Visit 2	Visit 3

• The visit will last approximately 2 hours.• Participants will come in and will be asked to complete the following:• Study consent form and related forms will be reviewed and signed.○ Hearing test will be completed (including otoscopy, tympanometry, speech testing (SRT and WRS), and pure-tone threshold testing (air and bone))• Earmold impressions taken	
• The visit will last approximately 2 hours.• Participants will come in and will be asked to complete the following:• Earmolds are fit to participants and hearing aids are programmed• Real ear measurements taken• Live sound quality and preference ratings task is completed.	
• The visit will last approximately 2 hours.• Participants will come in and will be asked to complete the following:• US Matrix test conducted• Streaming sound quality ratings task completed• At the end of data collection, participant will be debriefed and compensated for their time.

2.2 Determination of Sample Size

Our previous study (ID – 3167, NCT05521308) evaluated similar hearing aids programs (e.g., the current program vs. the proposed programs) and had a similar study design. Therefore, we have determined that a sample size of 20-25 participants, which is the sample we used for the previous study - ASQ study (SRF-3167), is sufficient for our purposes.

2.3 Statistical criteria of termination of trial

n/a

2.4 Planned Analyses

2.4.1 Datasets to be analyzed, analysis population

Datasets to be analyzed:

- Demographic / health care data information – age, sex, hearing thresholds
- Subjective ratings provided by participants when listening to acoustic or streaming signals
- Objective scores collected from speech in noise test

2.4.2 Primary Endpoint Analysis

The primary analysis focused on the subjective responses provided by participants during the acoustic task, comparing their experiences under different frequency response curves, hearing aid programs, and sound scenes. Scores for all 20 participants were tallied for the final analysis. Higher scores indicated a greater preference for a particular frequency response curve, while lower scores indicated a lesser preference. Additionally, the mean number of times participants preferred each frequency response curve (intervention) or rated the two interventions as equal in sound quality was calculated, based on the four sound quality attributes: comfort, noise intrusiveness, speech clarity (when applicable).

The analysis proceeded as follows:

1. **Chi-Square Analysis (First Step):** A chi-square test was conducted to compare the three means

(the mean number of times the standard curve was chosen, the mean number of times Variation #1 was chosen, and the mean number of times participants rated the sound quality as "same"). This test aimed to determine whether participants perceived a difference between the two curves by not selecting the "same" option.

2. **Chi-Square Analysis (Second Step):** Another chi-square test was conducted to compare the two means (the mean number of times the standard curve was chosen versus the mean number of times Variation #1 was chosen). This test assessed whether there was a preference between the two curves.

This process was repeated for each hearing aid program

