1.2 Primary Objective

The primary objective of this study was to evaluate whether participants with moderate to severe sensorineural hearing loss (SNHL) prefer a newly proposed frequency gain curve (Variation #1) compared to our current frequency response curve, when fitted with different hearing aid programs or under various hearing aid settings. Testing was conducted in a controlled lab environment, where participants listened to a range of stimuli to assess which program they preferred and how they rated each program based on various sound quality metrics.

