2.1 General

2.1.1 Design Type

This clinical investigation was an interventional study conducted at two investigation sites. The study involved a single group of participants who were tested under all conditions in a crossover design. During the live preference ratings, participants were blinded to the program they were using, although the investigator was aware of the program, as they programmed the hearing aids prior to testing. For the streaming sound quality task, participants wore headphones, and both participants and investigators were blinded to the program being rated.

The table below indicates the various programs that each participant evaluated.

Programs	Interventions
Acoustic Programs	
Program 1	Standard Frequency Response Curve
Program 1	Proposed Frequency Response Curve - Variation #1
Program 2	Standard Frequency Response Curve
Program 2	Proposed Frequency Response Curve - Variation #1
Program 3	Standard Frequency Response Curve
Program 3	Proposed Frequency Response Curve - Variation #1
Program 4	Standard Frequency Response Curve
Program 4	Proposed Frequency Response Curve - Variation #1
Streaming Programs	
Program 5	Current Streaming Frequency Response Curve – Variation #2
Program 5	Proposed Streaming Frequency Response Curve - Variation #3
Program 5	Proposed Streaming Frequency Response Curve - Variation #4
US Matrix Test Task Programs	
Program 1	Standard Frequency Response Curve
Program 1	Proposed Frequency Response Curve - Variation #1
Unaided	No hearing devices

Acoustic Task:

Participants were seated in the center of a 12-loudspeaker array, positioned at azimuths of 0°, 30°, 60°, 90°, 120°, 150°, 180°, 210°, 240°, 270°, 300°, and 330° in a sound-treated room. The 12 speakers were used to render ambisonic audio scenes. While immersed in these scenes, participants were asked to toggle between two frequency response curves: the standard curve and the proposed frequency response curve – Variation #1 – using an iPhone.

Participants were then asked to rate the following attributes for each program:

1. Which program resulted in increased noise intrusion?
2. Which program provided better speech clarity?
3. Which program offered greater comfort?
4. Which program did they prefer overall?

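### The primary chi-square tests use mean choice counts from repeated answers by the same 20 people, so their p-values cannot be interpreted, and step 1 does not answer its own question

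*Combined protocol and SAP*

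**What the plan says.** Section 2.1.1 describes repeated measurements on one group: "The study involved a single group of participants who were tested under all conditions in a crossover design". For each of four hearing aid programs, participants compare the standard curve with Variation #1 on noise intrusion, speech clarity, comfort and overall preference. The noise question reads "Which program resulted in increased noise intrusion".

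Section 2.4.2 states: "Scores for all 20 participants were tallied for the final analysis". It then forms the mean number of times each curve was preferred or the two were rated equal, "based on the four sound quality attributes: comfort, noise intrusiveness, speech clarity (when applicable"). Four attributes are announced and three are named. The section also mentions several sound scenes without giving their number.

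Two tests follow, repeated for each program:

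- Step 1 is a chi-square test on three means (standard, Variation #1, 'same'). Its purpose: "This test aimed to determine whether participants perceived a difference between the two curves".
- Step 2 covers the two curves only: "Another chi-square test was conducted to compare the two means".

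On direction, the section says: "Higher scores indicated a greater preference for a particular frequency response curve, while lower scores indicated a lesser preference". The plan states no averaging unit, expected values, significance level or method for repeated answers.

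**The concern.** There are three problems.

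1. **Scale.** Pearson's chi-square depends on the absolute size of its cells. Means have no fixed scale unless the divisor is known, so one data set can give very different p-values.
2. **Clustering.** Answers by one person to several questions and scenes are likely to be correlated. Treating them as independent counts overstates the information.
3. **Target.** Step 1 is meant to be about avoiding the 'same' option, but a three-cell test also responds to the split between the curves, and it rejects when 'same' is unusually frequent as well as when it is rare.

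The content of the mean is also open. If noise intrusion was pooled as worded, a choice that counts against a curve was added to choices that count for it.

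At stake is the inferential part of the primary objective. Depending on the reading, the tests either miss real preferences or declare preferences that are not there, and a reader cannot tell which.

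**Working it through.** The plan gives no significance level, effect size, power or test statistic here, so there is no figure of its own to reproduce.

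**Inputs.** From the documents: 20 participants, four questions, four programs. Assumed, because not stated: m = 4, 8, 12 or 16 answers other than 'same' per person per program; within-person correlation ρ = 0.1, 0.3 or 0.5; two-sided 5% level; equal expected values.

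**Effect of the divisor (step 2).** With two cells summing to N and an observed share p, chi-square = N(2p − 1)². For 70:30, (2 × 0.7 − 1)² = 0.16. Pooled totals give N = 20m; each other reading divides by its own unit.

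| Reading | Divisor k | N | m = 12: chi-square, p | m = 4: chi-square, p |
|---|---|---|---|---|
| (a) mean per participant | 20 | m | 1.92, 0.17 | 0.64, 0.42 |
| (b) mean per scene/attribute item | m | 20 | 3.2, 0.074 | 3.2, 0.074 |
| (c) mean over the four attributes | 4 | 5m | 9.6, 0.002 | 3.2, 0.074 |
| (d) pooled totals | 1 | 20m | 38.4, 6e-10 | 12.8, 0.0003 |

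The dependence on k is an algebraic fact; only the illustrative m and split are assumed.

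**False-positive rate (step 2).** With a true 50:50 split and beta-binomial answers, the exact distribution of the total over 20 people gives, across the assumed m and ρ:

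- (a) 0–0.2%
- (b) 0–1.2%
- (c) 0.05–17.5%
- (d) 9.5–50.6%

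With one scene (m = 4), (b) and (c) coincide at 0.05–1.2%, and (d) is 9.5–23%.

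A hand check uses the design effect D = 1 + (m − 1)ρ, with rejection probability close to P(|Z| > 1.96√(k/D)). For m = 16 and ρ = 0.5, D = 8.5. Reading (d) gives P(|Z| > 0.67), about 50%; reading (c) gives P(|Z| > 1.34), about 18%. Both agree with the exact results.

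A separate three-category simulation with 30% 'same' answers, m = 4, 8 or 16 and the same ρ gave 8.8–50.6% for step 2 on totals and about 0–1.1% on means (readings a and b).

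**Step 1 against its aim.** Three cells, equal expected values, 2 df, 20 answers, so each expected value is 6.67:

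- 0/0/20 (everyone says 'same'): chi-square = (6.67² + 6.67² + 13.33²)/6.67 = 40, p = 2e-9.
- 7/7/6 (70% report a difference): chi-square = (0.33² + 0.33² + 0.67²)/6.67 = 0.1, p = 0.95.

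The test rejects where nobody reports a difference and does not reject where most do.

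**Noise coding.** If noise intrusion was pooled unreversed, a true 70:30 benefit on every item is tallied as follows:

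- Four items: (3 × 0.7 + 0.3)/4 = 0.60. Then (2p − 1)² = 0.04, and chi-square falls fourfold. Under (b) it drops from 3.2 to 0.8, p = 0.37.
- The three named items: (2 × 0.7 + 0.3)/3 = 0.567. Then (2p − 1)² = 0.0178, a ninefold fall. Under (b) it drops from 3.2 to 0.36, p = 0.55.

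**Streaming (Section 2.4.3).** The same construction is used there. With 10 stimuli assumed, a 50/25/25 split at one rank level gives chi-square = 0.125N on 2 df. N = 10 (mean per participant) gives p = 0.54; N = 20 (mean per stimulus), p = 0.29; N = 200 (totals), p = 4e-6.

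**The case against.** The strongest reply has four parts.

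- **The worst figure fits the text least.** The section says means in both steps, so pooled totals, with up to 50.6% false positives, is the least natural reading. On most readings that use means, the harm is lost power. This stands, and it is why the conclusion is that the p-values cannot be interpreted, not that they are inflated.
- **There is a benign case.** With one scene per program and each attribute tested separately on raw counts, each person gives one answer. A chi-square test on 20 independent answers has a false-positive rate of about 4.1%. But this requires raw counts where the section specifies means, and a single scene where it speaks of several. Separate testing of attributes would, however, remove the noise-coding problem, as would favourable coding of that item.
- **The sizes rest on assumptions.** True of the error rates. They also use one common positive correlation; an unreversed noise item could be negatively correlated with the others and reduce the inflation under pooled totals. The divisor problem needs no such assumption. The step 1 examples need only equal expected values, and it is fair to say that a careful reader of 0/0/20 would see which cell dominates.
- **The study is exploratory and has no success rule.** This limits the consequences. It does not make the p-values meaningful, and no other test of the primary objective is planned.

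**Conclusion.** The concern holds and must be fixed. As written, the primary tests apply chi-square to averages with an unstated divisor and ignore repeated answers from the same 20 people. No reading consistent with the text is reliably calibrated. Under the stated assumptions (4–16 answers, correlation 0.1–0.5, equal expected values), means per participant or per item are very conservative, means over attributes can err either way, and totals give excess false positives. Step 1 does not test what it is said to test. The effect of noise coding is conditional on pooling without reversal. The tallies remain usable as description; the p-values do not.

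**What to change.** Label the re-analysis as a post hoc correction, and state the number of scenes and judgements per program, the items included and the coding of noise intrusion.

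- **Preference.** For each program, compute one score per participant from the overall-preference question: (Variation #1 choices − standard choices) / judgements, with 'same' counted as 0. Test the 20 scores against zero with a one-sample t-test and report the mean with a 95% CI. If there was only one judgement per person, use an exact sign test.
- **Attributes.** Analyse comfort, speech clarity where applicable, and reverse-scored noise intrusion separately in the same way. Section 1.2 covers them too: "to assess which program they preferred and how they rated each program based on various sound quality metrics".
- **Step 1.** Replace it with the participant-level share of 'same' answers and a 95% CI, described as reported difference, not as proof of perception.
- **Streaming.** Compare participant-level mean ranks within person.

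In simulation the t-test has a false-positive rate of about 5.0–5.3% with 4–16 answers per person, and about 5.0–5.7% with two or three judgements.

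The cost is SAP wording and a re-analysis of existing data. The p-values will be less favourable than from pooled totals. Power on overall preference alone (70:30, three scenes, correlation 0.3, all assumed) is about 69% with no 'same' answers (59–81% for correlation 0.5 to 0.1) and about 54% with 40% 'same' (49–62%). A correctly reversed four-question score would have about 84% and 78%, but would no longer measure preference alone. Four questions in four programs make up to 4 × 4 = 16 comparisons without multiplicity control, so the results should be presented as exploratory estimates.

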2.4.3 Secondary Endpoint Analysis

The secondary analysis focused on the subjective sound quality ratings provided by participants during the streaming task. Participants were asked to rank three stimuli in order of overall preference and sound quality, with each stimulus corresponding to one of the three frequency response curves being tested (Variations #2, #3, or #4). The analysis involved calculating the mean number of times each curve was ranked as the highest, lowest, and middle choice across all stimuli.

The analysis proceeded as follows:

1. **Chi-Square Analysis (First Step):** A chi-square test was conducted at each ranking level (highest, middle, and lowest) to determine how each frequency response variation was ranked.
2. **Chi-Square Analysis (Second Step):** Two additional chi-square tests were run at each ranking level to compare how the proposed frequency response curves (Variations #3 and #4) were ranked against Variation #1.

In total, 9 chi-square analyses were performed for this task.

For the speech-in-noise tests, the average SRT50 scores across all participants were compared to determine equivalence. Lower SRT50 scores indicate better performance.

1. **One-Way ANOVA:** A one-way ANOVA was conducted to assess the impact of the different interventions (standard curve, Variation #1, and unaided) on the SRT50 scores.
2. **Post-Hoc Analyses:** Post-hoc pairwise comparisons were conducted following the ANOVA, where one intervention was excluded at a time to assess differences between the remaining interventions.

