1.3 Secondary Objectives

One secondary objective of this study was to assess whether two newly proposed streaming frequency response curves (Variation #2 and Variation #3) are preferred by hearing aid users compared to our current streaming frequency response curve, across various musical genres and speech stimuli.

Another secondary objective was to evaluate the impact of the proposed frequency response curve (Variation #1) on speech performance in noise, specifically by comparing SRT50 scores to those obtained with the current frequency response curve. Participants will complete a standardized test (OLSA – US Matrix test) in noise within a sound booth, under three conditions: a program with the proposed frequency response curve, a program with the current frequency response curve, and an unaided condition (without hearing aids).

2 Design of the clinical investigation

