The responses were tallied for further analysis. This process was repeated for four different hearing aid programs, where the frequency response curves were compared but not the programs themselves. In other words, ratings from one hearing aid program were not compared with those from another.

Streaming Task:

Participants were asked to wear headphones while listening to three versions of the same pre-recorded stimulus: the Current Streaming Frequency Response Curve (Variation #2), the Proposed Streaming Frequency Response Curve (Variation #3), and the Proposed Streaming Frequency Response Curve (Variation #4). This process was repeated with multiple different stimuli. After listening to each version for each stimulus, participants were asked to rank them from most preferred to least preferred, with one version ranked in between. Responses were recorded on a laptop, and the rankings for each curve were tallied and compared at the end for further analysis.

US Matrix Test Task:

Participants were seated at the center of an 8-loudspeaker array positioned at azimuths of 0°, 45°, 90°, 135°, 180°, 225°, 270°, and 315° within a sound-treated room. Noise was presented from all speakers, except the one at 0° azimuth, while speech was presented from the front speaker at 0°. Participants were asked to repeat sentences they heard while wearing hearing aids programmed with either the Standard Frequency Response Curve or the Proposed Frequency Response Curve – Variation #1, or while wearing no hearing aids at all. A total of 20 sentences were presented for each condition. At the end of the experiment, a dB SNR (signal-to-noise ratio) score was calculated for each condition and used for further analysis.

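### The streaming rankings are tested one rank level at a time, which is not the head-to-head question in the objective, and there is no rule for when the highest and lowest levels disagree

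*Combined protocol and SAP*

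**What the plan says.** Section 1.3 sets the streaming objective: whether two new curves "are preferred by hearing aid users compared to our current streaming frequency response curve, across various musical genres and speech stimuli". Under the Streaming Task in section 2.1.1, listeners heard three versions of each stimulus, one with the current curve and two with proposed curves. After each stimulus, "participants were asked to rank them from most preferred to least preferred, with one version ranked in between". The task covered several stimuli ("This process was repeated with multiple different stimuli"), but their number is not given.

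Section 2.4.3 reduces these rankings to the mean number of times each curve was placed highest, middle and lowest. In the first step, "A chi-square test was conducted at each ranking level (highest, middle, and lowest) to determine how each frequency response variation was ranked". In the second, "Two additional chi-square tests were run at each ranking level to compare how the proposed frequency response curves (Variations #3 and #4) were ranked" against a comparator, which the text names as Variation #1. The stated total is nine tests. No level is named as decisive, no rule combines the levels, and no analysis uses the ranking as a whole.

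**The concern.** Every complete ranking of three curves shows directly whether a given proposed curve stands above or below the current one. That is the comparison the objective asks for, and the plan never tabulates it. The second step does not recover it, because it compares two counts within one rank level and does not ask who placed one curve above the other.

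A count at one level also depends on the third curve. If listeners who like the proposed direction divide their first places between two proposed curves, while listeners who like the current curve give it all of theirs, the current curve can lead at highest with minority support. The same listeners then put it last most often. A middle placement says nothing about which of two curves is preferred. At stake is whether a reader of the nine p-values can tell which curve was preferred, and whether a significant level test means any preference between proposed and current.

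**Working it through.** **The plan's own figure.** 3 levels × (1 three-way + 2 two-way tests) = 9, which matches section 2.4.3.

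**Inputs.** Three curves, fully ranked (section 2.1.1). N = 20, the number given for the primary analysis in section 2.4.2; section 2.2 plans 20-25. Assumptions: two-sided 5% level, independent rankings, one ranking per listener, and proposed curves (A, B) interchangeable with each other. C is the current curve.

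**Direction at each level.** Let p be the share ranking both A and B above C, with the rest ranking both below.
- Highest: A gets p/2 and C gets 1−p. A leads only if p > 2/3.
- Lowest: A gets (1−p)/2 and C gets p. A looks better once p > 1/3.
- Head-to-head: A beats C in a share p, so the balance point is 1/2.

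For p between 1/3 and 2/3 the highest and lowest levels therefore point in opposite directions.

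**Worked example, N = 20, p = 12/20.**

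| Level | C | A | B | Three-way p | A v C: chi-square, p |
|---|---|---|---|---|---|
| Highest | 8 | 6 | 6 | 0.82 | (1²+1²)/7 = 0.29, 0.59 |
| Middle | 0 | 10 | 10 | 0.007 | (5²+5²)/5 = 10, 0.0016 |
| Lowest | 12 | 4 | 4 | 0.041 | (4²+4²)/8 = 4.0, 0.046 |

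Head-to-head, A v C is 12:8, exact binomial p = 0.50, and the same for B v C. Mean ranks are 2.2 for C and 1.9 for A and B; Friedman p = 0.55. Two of the three pairwise level tests are significant, and one of those carries no direction. The direct comparison shows no clear preference.

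**Rejection rates when the head-to-head is truly 50:50.** Let s be the share of rankings that put A and B on the same side of C. The expected share of C is s/2 at highest and at lowest, and 1−s at middle. For A it is (1−s/2)/2 at highest and lowest, and s/2 at middle. Simulated rejection of one second-step test, 20 single rankings:

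| s | Expected highest C:A:B (%) | Expected middle C:A:B (%) | Reject at highest / middle / lowest |
|---|---|---|---|
| 1 | 50:25:25 | 0:50:50 | 25% / 100% / 25% |
| 0.9 | 45:27.5:27.5 | 10:45:45 | 14% / 57% / 14% |
| 0.8 | 40:30:30 | 20:40:40 | 8% / 19% / 8% |
| 2/3 (random order) | equal | equal | about 4% each |

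A head-to-head test on the same rankings rejects in about 4%.

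**Sensitivity to how counts are formed, at s = 1.** The plan tests means over an unstated number of stimuli, so the rates above are not those of the planned test.
- Raw counts pooled over independent rankings: the highest-level test rejects in 84% at 100 rankings and 99% at 200.
- Means over an assumed 10 stimuli with independent rankings: highest and lowest reject in about 1% or less, while middle still rejects almost always.
- If each listener gives the same ranking to all 10 stimuli, a mean per stimulus equals the single-ranking count, so the 25/100/25% rates return. A mean per participant halves the counts and gives about 6% at highest and lowest and 87% at middle.

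**The case against.** A reader might infer that the streaming objective goes unanswered however the tests fall. That is too strong. For three items, mean rank = 1·H + 2·(1−H−L) + 3·L = 2 − H + L, where H and L are the shares placed highest and lowest. The plan's own tallies therefore fix each curve's mean rank. A proposed curve that is more often highest and less often lowest than the current one has the better mean rank, and the results can be read that way. The ambiguity arises when the two levels disagree.

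A reader might also infer that the proposed curves did split the vote. No section says that they share listeners, and no results are given. With random ordering the level tests hold about their nominal rate, and the 25/100/25% figures need every listener to keep the current curve out of the middle.

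Nor are the tabulated rates the error rates of this trial's tests, for the reasons shown under the sensitivity check. Opposing results that are both significant are rare with few rankings: 0.7% at 20 rankings even with s = 1. In the worked example the highest-level result is p = 0.59. A curve that is both most often first and most often last may be a true description of divided listeners.

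Under complete indifference, at least one of the nine tests is significant in about 21% of trials with 20 rankings. That is a separate multiplicity matter and adds nothing here. Finally, section 1.1 calls the study exploratory, and streaming is a secondary objective.

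All of this limits reach and severity. It does not supply a head-to-head test or a rule for disagreeing levels.

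**Conclusion.** The concern holds in a limited form. The level-by-level tests address a different hypothesis from the one in section 1.3: equal counts at a rank level is not the same as no preference between a proposed curve and the current one. Followed exactly, the plan can give significant or opposing level results when the head-to-head preference is 50:50, and it does not say how to read them. The size depends on how far the two proposed curves draw on the same listeners, and on how counts are formed over stimuli; the documents give neither. For 20 single rankings the illustrative range is about 4% to 25% at highest and at lowest, and about 4% to 100% at middle. This should be fixed, but it does not affect the primary analysis and does not make every possible streaming result unreadable.

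**What to change.** First reconcile the labels. Section 2.1.1 calls the current streaming curve Variation #2 and the proposed ones #3 and #4; section 1.3 calls #2 and #3 the proposed curves; section 2.4.3 names Variation #1, the acoustic curve, as the streaming comparator.

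Then replace the nine tests in section 2.4.3 with two comparisons:
- For each participant, compute the share of stimuli in which the first proposed curve was ranked above the current curve, and likewise for the second.
- Test each set of participant shares against 0.5 with a signed-rank test, with Holm adjustment over the two tests.
- Report each mean share with a 95% confidence interval, and state the number of stimuli.
- Keep the highest, middle and lowest tallies as a descriptive table, with no preference conclusion drawn from them.

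Using one share per participant also avoids treating repeated stimuli from one listener as independent. Section 2.4.3 describes the tests as already performed, so label the new analysis post hoc if results are known. The cost is revised wording and a short re-analysis of rankings already recorded; no new data or participants are needed. What is lost is formal testing at separate rank levels, which does not answer the objective.

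### The streaming preference question is spread over nine chi-square tests with no stated alpha, adjustment, gate or deciding contrast; at 5% each on independent tallied rankings, about 21-24% of null studies give at least one false positive

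*Combined protocol and SAP*

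**What the plan says.** Section 1.3 asks whether two newly proposed streaming curves "are preferred by hearing aid users compared to our current streaming frequency response curve". That is two comparisons, each against the same reference.

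Section 2.4.3 sets out two steps:

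- Step 1: "A chi-square test was conducted at each ranking level (highest, middle, and lowest) to determine how each frequency response variation was ranked".
- Step 2: "Two additional chi-square tests were run at each ranking level". Their stated purpose is to set each proposed curve, numbered #3 and #4 here, against a comparator printed as Variation #1.

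It then gives the count: "In total, 9 chi-square analyses were performed for this task". No significance level appears anywhere in the document. For this task there is also no multiplicity adjustment, no rule making step 2 depend on step 1, and no rank level or contrast named as decisive. Section 1.1 calls the study exploratory.

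**The concern.** Two comparisons are needed and nine tests are run. Section 2.4.3 does not say which of them bears on the objective, does not call them descriptive, and does not limit what a significant one may support. A reader of the results could therefore take an isolated significant result at one rank level as an answer to the preference question, although the chance that some test is significant under no preference is well above the nominal rate. Some of the tests, notably those at the middle rank, have no clear preference direction at all.

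This is separate from the label problem in step 2. Correcting the comparator would still leave nine tests with no rule for reading them.

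**Working it through.** **Inputs from the document**

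- Rank levels: 3 (section 2.4.3).
- Participants: "Scores for all 20 participants were tallied for the final analysis" (section 2.4.2); section 2.2 planned 20-25.
- Stimuli: more than one per participant, number not given (section 2.1.1, streaming task).

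**Assumptions, because the document is silent or inconsistent**

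- 5% per test.
- Step 2 comparator read as the current streaming curve. Variation #1 is an acoustic curve and is not among the three that were ranked.
- Tallied counts as test input. Section 2.1.1 says rankings were tallied; section 2.4.3 speaks of mean counts.
- All rankings independent, with 1 to 20 stimuli per participant.

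**Count of tests.** 3 levels x 1 three-curve test + 3 levels x 2 pairwise tests = 3 + 6 = 9. This reproduces the plan's figure.

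**Independence reference.** 1 - 0.95^9 = 0.370. The nine tests share data, so the true figure is lower and has to be simulated.

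**Simulation under no preference** (200,000 studies per setting). Each ranking is a random ordering of the three curves. At each rank level, with N rankings and counts O:

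- three-curve statistic: sum of (O - N/3)^2 / (N/3), 2 df;
- pairwise statistic: (O_proposed - O_current)^2 / (O_proposed + O_current), 1 df.

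| Setting | Any of nine significant |
|---|---|
| 20 participants, 1 stimulus | 21.1% |
| 20 participants, 2 stimuli | 24.2% |
| 20 participants, 3-20 stimuli | 22.8-23.6% |
| 25 participants | 22.9-23.7% |

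The range is about 21-24%, which is 21/5 = 4.2 to 24/5 = 4.8 times the nominal 5%. The lowest value needs one stimulus per participant, which section 2.1.1 rules out.

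**What the total consists of**

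- Middle-rank tests alone contribute 5-6 percentage points.
- A false pairwise result favouring a proposed curve (more top ranks or fewer bottom ranks than current) occurs in about 7-9%. One two-sided 5% test would give 2.5% in that direction; two unadjusted top-rank contrasts would give 4-5%.
- If a pairwise result counted only when the three-curve test at the same level was also significant, about 10-11% of null studies would still show one.

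**Sensitivity to the assumptions** (20 participants)

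| Departure | Any of nine significant |
|---|---|
| Within-participant correlation 0.05, 5 stimuli | 32% |
| Correlation 0.05, 10 stimuli | 41% |
| Correlation 0.2, 5 stimuli | 53% |
| Correlation 0.2, 10 stimuli | 72% |
| Chi-square computed on mean counts | at most 0.04% |

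The 7-9% figure also rises with within-participant correlation. The near-zero last row is no reassurance: a chi-square on means is not a valid test of counts, and it would detect almost nothing.

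**Check of the proposed fix.** A participant-level Wilcoxon test of the two contrasts with Holm held the family-wise error at about 4% in null runs with correlated rankings. Head-to-head sign tests with the smaller p-value judged at 0.025 gave 2.3% (20 rankings) and 3.7% (200 rankings), with independent rankings.

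**The case against.** The best defence is that section 1.1 labels the whole study exploratory, the objective is secondary, and no success criterion is attached to it. On that view formal family-wise control is optional, and a sentence limiting interpretation would do. This stands as a reason for modest severity. It does not remove the point, because section 1.3 still poses a preference question and section 2.4.3 contains no such sentence.

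Three stronger readings are tempting, and the document does not support them.

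- *That the total of nine proves step 2 was ungated.* The count is reported retrospectively, and nine tests would also have been performed under a gate had all three step 1 tests been significant. What can be said is that no gate is stated and step 2 is worded unconditionally.
- *That 21-24% is the plan's error rate.* It depends on a 5% level the document never states, on counts as the input, and on independent rankings. Other readings run from about 0% to above 70%.
- *That any of nine false positives would be a false claim for a proposed curve.* A middle-rank result, or one favouring the current curve, does not show that a proposed curve is preferred. On that narrower question the figure is 7-9%. At matched settings this is less than twice what two unadjusted top-rank contrasts would give.

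It is also fair to object that contrasts chosen now cannot restore prespecified error control, since the document describes the analyses as already done. That is correct, and the fix has to disclose it.

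**Conclusion.** The point holds with modest weight. Section 2.4.3 answers a two-comparison question with nine tests and gives no alpha, adjustment, gate or deciding contrast. With 5% per test, tallied counts, independent rankings and the current streaming curve as comparator, at least one test is falsely significant in about 21-24% of null studies. A false result favouring a proposed curve at the top or bottom rank arises in about 7-9%. Independence is the doubtful assumption: each participant ranked several stimuli, and correlation among those rankings raises both figures. The exploratory label and the secondary status of the objective keep this to a change that should be made, not one on which the study's main conclusion turns.

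**What to change.** 1. Reconcile the variation numbers first. Section 1.3 calls the proposed streaming curves #2 and #3. Section 2.1.1 gives #2 to the current curve and #3 and #4 to the proposed ones, and section 2.4.3 also has #3 and #4 as proposed but names #1 as the step 2 comparator.
2. In section 2.4.3, name two deciding contrasts by role: each proposed streaming curve versus the current streaming curve.
3. For each contrast, compare the participant's mean rank over stimuli by a Wilcoxon signed-rank or sign test. This makes the participant the unit of analysis, so correlation between one person's rankings does not inflate the error. Apply Holm to the two at a family-wise two-sided 5%.
4. Report the highest, middle and lowest tallies descriptively, without p-values, and say that no preference claim rests on them.
5. Disclose that the contrasts were chosen after the analyses had been described as performed, so the re-analysis is a revision and not prespecified.

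The cost is revised wording and a re-run on existing data, with no new participants. The smaller of the two p-values must fall below 0.05/2 = 0.025, and isolated rank-level results can no longer be claimed.
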